## **3.0 STUDY DESIGN**

We will use an effectiveness-implementation hybrid study design that allows for simultaneous study of the clinical effectiveness and implementation of distress screening to address the need for evidence in both areas. Hybrid designs have *a priori* focus on assessing outcomes relevant to both effectiveness of an intervention and implementation-related outcomes. We will employ a sequential mixed methods study design that integrates qualitative and quantitative methods, as is appropriate to address the proposed research questions. Our highly pragmatic approach is guided by the Pragmatic-Explanatory Continuum Indicator Summary-2 with adaptive workflow design. We will use the Consolidated Framework for Implementation Research (CFIR) to guide collection and analysis of implementation outcomes.

[figure not shown]
We will use cluster randomization at the medical center level. There will be 6 KPSC medical centers participating in total: 3 intervention sites and 3 control sites.

The screening program will be implemented at the 3 intervention sites, offering the program to all newly diagnosed breast cancer patients within the intervention site over a 12-month period with no exclusions. Under the intervention condition, distress screening using the Patient Health Questionnaire (PHQ), available in the electronic record, will be offered to patients in clinic (paper-based surveys or completed online with the assistance of the LVN, MA, RN or other member of the clinical team administering the screening). Patients are free to refuse distress screening.

Control condition patients will receive the current standard of care (ad hoc distress screening at the clinician's discretion) and basic education about the study. Control sites will not be prohibited from using the PHQ. We anticipate a total sample of 1,200 newly diagnosed patients, 600 in each arm.

Intervention sites will receive audit and feedback of performance data and implementation facilitation throughout the 12-month intervention period (implementation strategies).

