#### **14.0 STATISTICAL CONSIDERATIONS**

**Aim 1: Evaluate the effectiveness of a guideline-recommended distress screening program for breast cancer patients in improving identification of distressed patients, initiation and completion of referrals to behavioral health, and patient-reported and utilization outcomes as compared to usual care within KPSC, using a pragmatic cluster randomized control trial design.**

- 14.1 **Power and sample size.** Of the 14 KPSC medical centers, we have selected 6 centers with the highest average number of new breast cancer cases diagnosed between 2011 and 2014. Based on the average number of cases. We expect a total of at least 1,200 newly diagnosed patients across the 6 sites, and to enroll anywhere from 50 to 300 newly diagnosed breast cancer patients per intervention site, entering all such cases into our cohort with no exclusions. We performed cluster randomization to select the intervention and control sites. While cluster randomization may be less statistically efficient than individual randomization, we believe it makes the study more feasible for several reasons. First, it allows us to truly evaluate the effectiveness of the distress screening program, with the screening offered to all newly diagnosed patients in the intervention centers. This will provide real-world information on uptake and effectiveness. Second, it allows us to avoid contamination between the distress screening intervention and other possible competing interventions, as well as outside information that may be publicly available to patients. Third, it allows us to balance (on average) medical center-level factors that we are otherwise unable to measure reliably. For all outcomes, we expect relatively small standardized effect sizes (measured in terms of z-scores) ranging from 0.2-0.4, because this is an effectiveness study. To achieve 80% power with a significance level of 0.05, our per-center sample size requirement ranges from as few as 20 for large effect size (0.4) and zero intraclass correlation (ICC), to about 400 for small effect size

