and large ICC (0.2 and 0.01, respectively). Given that we can expect 50 to 300 newly diagnosed breast cancer patients per center, we should be adequately powered to detect effect sizes as small as 0.2, given ICCs no greater than 0.007. This is a lower bound on our power, since we expect to have as many as 200 more patients at some medical centers, and so our power is most likely greater than reported here.

- 14.2 Statistical analysis plan: All variables will be described with summary statistics appropriate for measurement type, such as frequency and percent, mean, median, standard deviation, minimum, and maximum. Patterns of missing values will be examined and evaluated for randomness using the method described by Enders. Diagnostic plots and inferential tests for tenability of assumptions will be evaluated for our primary and secondary outcomes, and appropriate remedial methods (e.g., Box-Cox transformations) applied where required. We will analyze referral and utilization outcomes as the total amount of services used during the study period, and use said diagnostic tests to determine the best modeling strategy for examining relationships with relevant demographic and clinical characteristics, exploring potential disparities by race/ethnicity and socioeconomic status. If necessary, we will analyze relationships with referral and utilization outcomes using Poisson or Negative Binomial regression models. We will use an intent-to-treat analysis, including data on all newly diagnosed patients in the intervention and control groups without regard to their screening status, appropriate for a cluster RCT.

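### Section 14.1 claims 80% power for an effect of 0.2 at ICCs up to 0.007; with 3 centres per arm and 200 patients per centre, power at ICC 0.007 is about 40% to 61%

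*Combined protocol and SAP*

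**What the plan says.** Section 3.0 fixes the design: "There will be 6 KPSC medical centers participating in total: 3 intervention sites and 3 control sites". It also gives the size: "We anticipate a total sample of 1,200 newly diagnosed patients, 600 in each arm", an average of 200 per centre. Section 14.1 agrees on the number of centres: "we have selected 6 centers with the highest average number of new breast cancer cases diagnosed between 2011 and 2014".

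Section 14.1 expects standardized effects of 0.2 to 0.4 for every outcome and makes three numerical claims:

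- For 80% power at the 0.05 level, the section says that "our per-center sample size requirement ranges from as few as 20 for large effect size (0.4) and zero intraclass correlation (ICC), to about 400". The figure of 400 belongs to effect 0.2 and ICC 0.01.
- With 50 to 300 patients expected per centre, the section concludes that "we should be adequately powered to detect effect sizes as small as 0.2, given ICCs no greater than 0.007".
- It then treats the resulting power as a minimum, on the ground that some centres may be larger: "This is a lower bound on our power, since we expect to have as many as 200 more patients at some medical centers".

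The section does not give the formula, the software, the sidedness of the test or the number of centres per arm used in the calculation.

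**The concern.** With three centres per arm, between-centre variation sets a limit on precision that more patients cannot remove. A requirement of 400 per centre at ICC 0.01, and adequate power at ICC 0.007, both look too good for so few centres.

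The figure of 20 can be doubted without any ICC. Twenty per centre in three centres is 60 per arm, yet an individually randomized trial needs about 98 per arm at effect 0.4.

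The low end of the expected effect range is at stake. Referral, utilization and patient-reported outcomes all rest on this one power statement. Anyone who takes the 80% at face value will read a non-significant result as stronger evidence against an effect of 0.2 than the design can supply.

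**Working it through.** **Inputs.** Significance level 0.05, power 80%, effects 0.2 and 0.4 in SD units, ICC 0, 0.007 and 0.01 (section 14.1); 3 centres per arm and 200 patients per centre on average (section 3.0). Assumptions: two-sided test and equal centre sizes, except where varied below.

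**Formula.** With k centres per arm and m patients per centre, the standard error of the arm difference is

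SE = √[2(1 + (m − 1)·ICC) / (k·m)].

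Power is found (a) from the normal distribution and (b) from the noncentral t with 2k − 2 degrees of freedom.

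**Step 1: trying to reproduce the plan's figures.**

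| Plan's figure | 3 per arm, normal | 3 per arm, t (4 df) | 6 per arm, t (10 df) |
|---|---|---|---|
| 20 per centre (effect 0.4, ICC 0) | 32.7 | 58.9 | 20.1 |
| about 400 per centre (effect 0.2, ICC 0.01) | none; ceiling 68.8% | none; ceiling 46.3% | 411 |
| per-centre number at effect 0.2, ICC 0.007 (not stated) | 1,541 | none; ceiling 59.9% | 184 |
| largest ICC at effect 0.2 (0.007 stated), taking 200 per centre | 0.0027 | none; 73.7% at ICC 0 | 0.0074 |

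The ceilings come from letting m grow without limit, so that SE tends to √(2·ICC/k). For ICC 0.01 and k = 3 this is √(0.02/3) = 0.0816, and 0.2/0.0816 = 2.45. The normal method needs 1.96 + 0.84 = 2.80 for 80% power, so no m is large enough.

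The first entry by hand: 2 × 2.80² / 0.4² ≈ 98 per arm, and 98/3 ≈ 33 per centre.

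Only the last column matches all the stated figures. Five per arm with the normal method comes near (19.6, 361, 173) but fits less well. Six per arm with the normal method does not fit (16 and 187 for the first two rows).

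**Step 2: power of the actual design at the claimed limit.** For k = 3, m = 200 and ICC 0.007:

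SE = √[2(1 + 199 × 0.007)/600] = √(4.786/600) = 0.0893, and 0.2/0.0893 = 2.24.

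- Normal: Φ(2.24 − 1.96) = 61.0%.
- Noncentral t, 4 df, critical value 2.776: 40.2%. A simulation of 200,000 trials gave 40.4%.

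The effect detectable with 80% power is 2.80 × 0.0893 = 0.25 (normal) or 0.34 (t). At ICC 0.01 these are 0.28 and 0.38.

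**Step 3: the lower-bound statement.** Take the top of the plan's range plus 200, that is 500 patients, at every centre. At ICC 0.007, power for 0.2 is then 73.4% (normal) or 50.2% (t), still below 80%. Unequal sizes move it the other way. With an illustrative 100, 200 and 300 in each arm (1,200 in all), the mean variance of a centre mean is 0.007 + 0.993 × (1/100 + 1/200 + 1/300)/3 = 0.01307. SE is then √(2 × 0.01307/3) = 0.0933, and t-based power for unweighted centre means is about 38%, against 40% with equal sizes.

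**Step 4: survey outcomes.** Section 4.8 limits surveys to English- or Spanish-speaking patients who agree to take part. The plan gives no response rate. At an assumed 50% (100 respondents per centre), ICC 0.007 and a single time point, the detectable effect is 0.30 (normal) or 0.40 (t).

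**The case against.** The strongest points on the other side are these.

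- **The ICC of 0.007 is a limit, not an expectation.** This is fair. At 200 per centre the normal method gives 93% at ICC 0 and stays at or above 80% up to ICC 0.0027. But the plan's claim extends to 0.007, where both methods fall short, and the t method stays below 80% even at ICC 0.
- **The upper part of the effect range is covered.** This is largely so. At ICC 0.007 and 200 per centre, power is 92% (normal) or 71% (t) for 0.3, and 99% or 91% for 0.4. The shortfall lies at the low end, which is the end the plan names.
- **The t reference on 4 df is not prescribed by the plan.** True, so both results are shown. The t method is nevertheless the one that reproduces the plan's own figures, which makes 40% the like-for-like value.
- **The test might be one-sided.** Power is then 72% (normal) or 58% (t). At effect 0.4 and ICC 0 the requirement is 26 or 39 per centre, not 20, and ICC 0.01 still never allows 80% (ceilings 78.9% and 64.5%).
- **The cause is inferred.** It is. The finding does not depend on it, because no version with 3 per arm gives the stated figures.
- **Repeated surveys or covariate adjustment could recover some precision.** Possibly, but 14.1 claims no such gain. The survey figures above do ignore the repeated measures.

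**Conclusion.** The power statement is wrong for the design as written. With 3 centres per arm, 200 per centre, ICC 0.007 and a two-sided 0.05 test, power for an effect of 0.2 is 40% (t, 4 df) to 61% (normal), against the 80% claimed. None of the planning figures of 20, about 400 and 0.007 survives under either method, and the one for effect 0.2 at ICC 0.01 has no solution. The lower-bound sentence also fails.

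Equal centre sizes are assumed for the main figures; unequal sizes would reduce power somewhat. At an ICC well below 0.007 the shortfall shrinks, and by the normal method it disappears below about 0.0027. Entry of the 6 centres as a per-arm number is the likely explanation but cannot be confirmed from the document. The text must be corrected, since it credits the trial with a sensitivity it does not have.

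**What to change.** Rewrite section 14.1 for 3 centres per arm, naming the formula, sidedness, reference distribution, ICC and centre size.

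- State that at 200 per centre and ICC 0.007, power for 0.2 is about 40% (t, 4 df), with 61% by the normal approximation shown beside it, and that the effect detectable with 80% power is about 0.34 (normal: 0.25).
- Replace the figure of 20 with about 59 (normal: 33). State that effect 0.2 at ICC 0.01 cannot reach 80% at any centre size.
- Delete the lower-bound sentence.
- Give a separate detectable effect for survey outcomes at the number of respondents expected.

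The cost is the rewording of one section and a less favourable power statement. No centres or patients need be added.

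### Section 14.1 calls its power a lower bound, but the figure describes centers of about average size with almost no margin and is not a floor

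*Combined protocol and SAP*

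**What the plan says.** Section 14.1 (Power and sample size) expects "relatively small standardized effect sizes (measured in terms of z-scores) ranging from 0.2-0.4" for all outcomes. It gives a per-center requirement at 80% power and significance level 0.05 of "as few as 20 for large effect size (0.4) and zero intraclass correlation (ICC), to about 400 for small effect size"; the upper figure belongs to an effect of 0.2 with an ICC of 0.01. Its conclusion begins: "Given that we can expect 50 to 300 newly diagnosed breast cancer patients per center, we should be adequately powered to detect effect sizes as". That sentence goes on to put the smallest detectable effect at 0.2, provided the ICC does not exceed 0.007. The next sentence is the one at issue: "This is a lower bound on our power, since we expect to have as many as 200 more patients at some medical centers". It ends by saying that power is probably higher than the figure reported.

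On size, Section 14.1 expects at least 1,200 patients over the 6 sites, and "to enroll anywhere from 50 to 300 newly diagnosed breast cancer patients per intervention site". Section 3.0 says "We anticipate a total sample of 1,200 newly diagnosed patients, 600 in each arm", with 3 intervention and 3 control sites. Section 14.1 does not give the formula, the number of centers used in it, the center size behind the 0.007 limit, or any allowance for unequal centers.

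**The concern.** A lower bound on power has to hold at the unfavourable end of the inputs it covers. The inputs here are centers of 50 to 300 patients, averaging about 200. If 80% is reached only when centers are near that average, the figure is a central estimate, and a modest shortfall takes it below 80%.

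Readers are told that any error lies on the safe side. If that is untrue, a null result for an effect of 0.2 SD could be read as stronger evidence of no benefit than the design can give.

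**Working it through.** **Inputs.** Effect d = 0.2 to 0.4 (SD 1), 80% power, alpha 0.05, ICC 0 to 0.01, limit 0.007, centers of 50 to 300 (Section 14.1); 1,200 patients in 6 centers, 3 per arm (Section 3.0). The average is 1,200/6 = 200. Sidedness is not stated; two-sided is assumed because it fits the printed figures.

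**Formula.** A center of size m contributes effective size m/[1 + (m − 1)ICC]. Let I be the sum of these over the centers of an arm. Then SE = √(1/I₁ + 1/I₂) and the noncentrality is d/SE. Power comes from the noncentral t with (number of centers − 2) df, or from the normal approximation.

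**Step 1: reproduce the plan's figures.** Normal and t versions, one- and two-sided, were tried with 3 to 7 centers per arm. Two-sided results, patients per center for 80% power:

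| Variant | d 0.4, ICC 0 (plan: 20) | d 0.2, ICC 0.01 (plan: about 400) | d 0.2, ICC 0.007 |
|---|---|---|---|
| t, 6 per arm | 20.1 | 411 | 183.6 |
| normal, 5 per arm | 19.6 | 361 | 173 |
| normal, 3 per arm | 32.7 | not reachable | 1,541 |
| t, 3 per arm | 58.9 | not reachable | not reachable |

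The first row fits best. The second is the nearest alternative, and it also puts the 0.007 limit near the average center size.

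**Step 2: power by center size on the best-fitting variant** (6 per arm, t on 10 df, d = 0.2, ICC 0.007). At m = 200, effective size = 200/(1 + 199 × 0.007) = 200/2.393 = 83.6; I = 6 × 83.6 = 501.5; SE = √(2/501.5) = 0.0632; noncentrality = 0.2/0.0632 = 3.17; power 81%. In the same way:

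- 100 per center: 67%
- 150 per center: 76%
- 184 per center: 80%
- 200 per center: 81%
- 300 per center: 87%

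The largest ICC that keeps 80% at 200 per center is 0.0074, so the printed 0.007 is close to what the average center size allows.

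**Step 3: the 200 extra patients.** If the base is 184, then 184 + 200 = 384, outside the plan's range. If the base is 100, so that 100 + 200 = 300 fits the range, power at the base is 67%. On this variant neither base gives both 80% power and a top size within the range.

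**Step 4: unequal sizes at an average of 200** (same formula, efficient weighting, each triple used twice per arm; 81.4% if equal):

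- 150/200/250: 81.0%
- 100/200/300: 79.7%
- 50/250/300: 77.2%

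The loss is 0.4 to 4.2 points. Inequality alone is a small effect; the thin margin above 80% is what makes it count.

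**Step 5: the design as randomised** (3 per arm, d = 0.2, ICC 0.007). At 200 per center, I = 3 × 83.6 = 250.7; SE = √(2/250.7) = 0.0893; noncentrality = 2.24. Power is 40% (t, 4 df) to 61% (normal). At 300 in every center it is 45% to 67%, so 80% is not reached even at the top of the stated range.

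**The case against.** The best counter-argument is that 1,200 is stated as a minimum and the 200 are additional patients. With efficient weighting, added patients never lower power: on the best-fitting variant, raising one center in three from 184 to 300 moves power from 80.0% to 82.5%. This stands. A reader might infer that the plan's reasoning runs in the wrong direction because more patients at some centers must mean fewer at others. The documents do not compel that, since the total is not fixed. What is missing is a base size at which 80% is a floor.

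Three other strong readings also fail:

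- **Fifty patients in every center.** The formula gives 48%, but six such centers hold 300 patients against an expected minimum of 1,200, and the sites were chosen as the highest-volume ones. It marks the low end of the range and is not an expected case.
- **Arms of 900 and 300.** This conflicts with the 600 per arm anticipated in Section 3.0.
- **80% only if centers are roughly equal.** This is false: 100/300/300 gives 81.7%.

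It is also fair to say that the formula is inferred, and that with 6 centers per arm an average of 200 would mean 2,400 patients. The comparison of 184 with 200 is therefore per center, and the point is not wholly separable from the number of centers. The plan's closing words are hedged as well, speaking of likelihood. None of this supplies a reason to call the figure a bound.

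**Conclusion.** The lower-bound claim is not supported. On the variant that best reproduces the plan's own numbers, 80% power at effect 0.2 and ICC 0.007 needs about 184 patients in every center, against an expected average of 200. The margin is about one percentage point, and a fall to 150 per center gives 76%. The figure is an average-case value. For the six centers actually randomised, 80% is not a floor either: 40% to 61% at 200 per center, depending on the reference distribution.

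This rests on a two-sided 5% test, efficient weighting of centers and, for the 184, an inferred formula. The 40% to 61% range does not depend on that inference. The number of centers is the larger problem, and the two are best corrected together.

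**What to change.** In Section 14.1:

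1. Delete the lower-bound sentence, including its closing clause that power is probably higher than reported.
2. Recompute power for the 6 randomised centers, 3 per arm, from their own expected counts (the 2011–2014 case data used to select them). Sum mᵢ/[1 + (mᵢ − 1)ICC] by arm as allocated, and state the formula and degrees of freedom.
3. Report the result as expected power, with a lower figure for a plausible shortfall. As an illustration, 150 per center with 3 per arm gives 36% (t) to 56% (normal) at effect 0.2 and ICC 0.007.
4. Limit the adequacy claim for an effect of 0.2 to the effect sizes, ICCs and center sizes for which it holds.

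The cost is one deleted sentence and a short recalculation from counts already in hand. No patients or data are added. The downside is that the stated power becomes less favourable and can no longer be called conservative.

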- 4.8 **Identification of participants for patient-reported outcome surveys.** All eligible patients who speak English or Spanish will be invited to participate in a survey of patient-reported outcomes. We will confirm if the potential participant has an active email address via our membership databases. Those who do will be initially contacted via email; those who do not will be initially contacted via postal mail (see contact workflow descriptions, below). Those who agree to participate will be asked to complete these two brief surveys at 3 time points (3-, 6- and 12-months). We will alert the oncology teams at all participating medical centers, as well as KPSC Member Services, in advance so that they are aware of the survey administration schedule and prepared to address any patient questions about the surveys and/or the study.
- 4.9 **Survey administration and tracking:** We will use RedCap software for all recruitment and survey tracking, as well as for on-line consenting and administration of the surveys whenever possible (e.g., for all patients with a viable email address), as well as for tracking postal mail and phone recruitment contact attempts.
- 4.10 **Outcomes:**

Primary. Our primary outcome is percent of eligible patients screened and referred (based on PHQ score) at intervention versus control sites.

Secondary. Our secondary outcomes include: completion of recommended referrals, utilization of outpatient medical oncology visits, primary care visits, behavioral health visits, urgent care visits, and emergency department visits; we will also examine patient-reported outcomes using the Functional Assessment of Cancer Therapy-Breast survey, and the Breast Cancer Prevention Trial (BCPT) Symptom Checklist.

***Please note: We received a waiver of written informed consent for the electronic health record data collection aspect of the study to identify newly diagnosed breast cancer patients at intervention and control sites during the screening intervention period (12 months) on September 22, 2016; we received a waiver of written informed consent for the survey portion of the study on May 8, 2017.***

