## **12.0 CRITERIA FOR EVALUATION AND ENDPOINT DEFINITIONS**

- **Distress screening:**
  - PHQ instrument was completed by the patient either during an oncology-related visit or online within 10 days pre- or post-visit.
  - Score of PHQ (continuous) and categorized to low, medium, high score
- **Utilization:**
  - Number of urgent care visits and associated diagnostic codes
  - Number of emergency department visits and associated diagnostic codes; subsequent discharge or hospitalization
  - Hospitalizations, length of stay, and associated diagnostic codes
  - Primary care visits
  - Medical oncology visits
  - Behavioral health visits
  - Number of referrals to behavioral health services
- **Patient-reported outcomes:**
  - Fact-B Functional Well-Being (Likert scale, 0-28)
  - Fact-B Social/Family Well-Being (Likert scale, 0-28)
  - Fact-B Emotional Well-Being (Likert scale, 0-24)
  - Fact-B Functional Well-Being (Likert scale, 0-28)
  - Breast Cancer Subscale (Likert scale, 0-40)

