Patient-reported outcomes from our mailed patient surveys (FACT B and BCPT) will be subjected to the same diagnostic testing as the utilization outcomes. To account for having repeated measurements for these patient-reported outcomes (3, 6, and 12 months post-diagnosis), we will use generalized estimating equations or linear mixed effects models, for situations where no or some repeated measures are missing, respectively. We will also analyze patient-reported outcomes using non-parametric regression techniques, such as quantile regression, to assess the sensitivity of our findings to other key modeling assumptions. Additionally, to analyze any improvement in identification of highly distressed patients by the systematic screening program, we will compare patients reporting high levels of distress on the FACT-B with patients receiving referral for high-level distress services (psychiatry, psychology). Statistical analyses will be conducted using SAS, R and/or MPlus. The study team will meet regularly to review adherence to the study protocol, evaluate study progress, and identify and resolve issues. Frequencies tables will be examined and out-of-range checks of all variables will be conducted, and results checked for consistency. Our advocate and advisors will provide insights and suggestions to guide our analyses to ensure we are considering a broad range of views

**Aim 2: Identify patient-, clinician-, and system-level barriers and facilitators to implementation of the program, and assess stakeholder-perceived acceptability, fidelity, and achievements of the program**

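### The primary outcome is a percent of patients, but section 14.2 names no between-arm analysis of that percent, and the models it names for referral are for totals

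*Combined protocol and SAP*

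**What the plan says.** Section 4.10 states: "Our primary outcome is percent of eligible patients screened and referred (based on PHQ score) at intervention versus control sites". Each eligible patient either meets this or does not.

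Section 14.2 describes the handling of referral in these words: "We will analyze referral and utilization outcomes as the total amount of services used during the study period". It adds: "If necessary, we will analyze relationships with referral and utilization outcomes using Poisson or Negative Binomial regression models". The analysis set is all newly diagnosed patients in both arms, by intent to treat. Generalized estimating equations and mixed models appear only for the repeated patient surveys. No logistic, binomial or other comparison of proportions between arms is named, and no model for referral carries a center term.

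Two other statements touch on referral. Section 14.2 opens with description: "All variables will be described with summary statistics appropriate for measurement type, such as frequency and percent". Later it plans to set patients with high FACT-B distress against patients referred to psychiatry or psychology.

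Among the endpoint definitions in section 12.0, referral appears once, under Utilization: "Number of referrals to behavioral health services". The combined outcome of section 4.10, screened and referred, is not defined there.

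**The concern.** A reader who follows section 14.2 to analyse referral obtains a contrast in the number of referrals. The primary outcome asks what share of patients were screened and referred. A patient with three referrals counts three times in the first and once in the second.

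The design gives reasons for the two to separate:

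- Section 4.3 encourages repeat screening at follow-up visits at intervention sites, and section 4.6 attaches a referral route to every PHQ category, including the low one. Repeat referrals could therefore be more common in that arm.
- Section 5.2 draws referrals from a database of all referral activity. A control patient referred without a PHQ adds to the total but is not screened and referred. This works in the other direction, so the sign of the discrepancy cannot be fixed in advance.

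At stake is whether the main result of the trial estimates its own primary outcome, and whether its method is chosen before the data are seen.

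**Working it through.** **Plan figures.** There is none to reproduce on this point. The documents give no expected percent referred and no number of referrals per patient; section 14.1 works in standardized effects of 0.2 to 0.4 for all outcomes.

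**Inputs from the documents.** 600 patients per arm and 3 centers per arm (section 3.0).

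**Assumed inputs.** 20% or 40% referred, the same in both arms; 1 referral per referred control patient; 1, 1.5 or 2 per referred intervention patient.

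**Identity.** Mean referrals per patient = (percent referred) × (mean referrals per referred patient). Hence

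count ratio = (ratio of percents) × (ratio of referrals per referred patient).

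Only the first factor on the right concerns the percent of patients.

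**Numbers at 20%.** Referred patients per arm: 600 × 0.20 = 120.

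- Control total: 120 × 1 = 120.
- Intervention total at 1.5 each: 120 × 1.5 = 180; ratio 180/120 = 1.5.
- Intervention total at 2 each: 120 × 2 = 240; ratio 240/120 = 2.0.
- Difference in percent in both cases: 20% − 20% = 0.

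At 40% the totals are 240 versus 360 or 480, and the ratios are again 1.5 and 2.0.

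**Simulation.** 400 runs per scenario, 600 per arm, equal percents, no clustering. Entries are the share of runs with p < 0.05.

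| Percent referred, both arms | Referrals per referred patient (control, intervention) | Mean count ratio | Test of percent | Poisson | Negative Binomial |
|---|---|---|---|---|---|
| 20% | 1, 1 | 1.00 | 5.5% | 3.0% | 3.0% |
| 20% | 1, 1.5 | 1.52 | 4.5% | 91.8% | 88.5% |
| 20% | 1, 2 | 2.01 | 5.0% | 100% | 100% |
| 40% | 1, 1 | 1.01 | 5.0% | 0.8% | 0.8% |
| 40% | 1, 1.5 | 1.51 | 4.0% | 100% | 100% |
| 40% | 1, 2 | 2.02 | 6.0% | 100% | 100% |

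The count models are not at fault here: they detect a real difference in totals. It is simply not a difference in the primary outcome. Because clustering is left out, these rates show that the two targets differ; they are not the operating characteristics of this trial.

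**Degrees of freedom for a center-level comparison.** 6 centers − 2 arms = 4.

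**The case against.** The best defence is that the totals sentence was never meant for the primary outcome. Section 12.0 has a count endpoint for referrals, and section 5.2 plans to compare their number; a total is the right analysis for that. The sentence goes on to speak of relationships with demographic and clinical characteristics and of disparities, not of a test between arms. It also covers no screening variable, although the primary requires screening as well as referral. This reading is plausible. It removes the conflict but leaves the primary outcome with no inferential analysis, so the gap stands on either reading.

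A reader might go further and infer that totals are the sole treatment of referral in the plan. They are not: the percent could be described by arm under the general summary rule, and the FACT-B comparison also uses referral. Neither supplies a between-arm estimate of the primary percent with an interval or test.

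A reader might also object to the phrase "appropriate remedial methods (e.g., Box-Cox transformations) applied where required", since section 14.2 attaches it to primary and secondary outcomes alike. It is one conditional example. Applied to a yes/no variable it only rescales two values, which is useless but harmless, so nothing here rests on it.

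**Conclusion.** The point holds in this form: section 14.2 names no between-arm analysis of the primary percent, and the models it does name for referral are for totals, without a center term. Under the assumed inputs, equal percents go with a count ratio of 1.5 or 2.0. The identity holds whatever the inputs; the size of any discrepancy depends on referral rates that the documents do not give.

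A reader might infer that the two analyses will point in opposite directions. Arithmetic allows it: 120 patients (20%) with 1 referral each give 120, and 90 patients (15%) with 2 each give 180, so the count ratio is 1.5 while the percent falls by 5 points. No figure in the documents makes that case likely. Nor do they show that the investigators intend to report totals as the primary result. The plan should be corrected because it leaves the question open.

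**What to change.** In section 14.2:

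- Define the primary outcome as one yes/no per eligible patient, screened and referred, over all eligible patients in both arms, and carry the same definition into section 12.0.
- Name one between-arm estimate of the difference in percent that suits 3 centers per arm. Examples are the difference in mean center proportions with a 95% CI on 4 df, or a binomial mixed model with a center random intercept and small-sample degrees of freedom.
- Keep total referrals and visits as secondary count outcomes, with a center effect and an offset for follow-up time. Section 5.3 gives 18 months of utilization data only as a maximum; a patient who enters at the end of the 12-month period has 18 − 12 = 6.

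The cost is wording: the data are the same and the software is standard. The downside is a wider, more honest interval. With 4 df the t multiplier is 2.776 against the normal 1.960, so for the same standard error the interval is 2.776/1.960 = 1.42 times as wide.
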